6.1.1 Dosing regimen

This is a single arm study. All patients except those with impaired liver function will be administered a dose of 10 mg Afinitor[®] orally once daily (Table 6-1) at the same time every day, either consistently with or without food.

Medication labels for study drug will comply with the legal requirements in China and be printed in local language. They will supply no information about the patient. The storage conditions for study drug will be described on the medication label.

Table 6-1 Dose and treatment schedule

Study treatment	Pharmaceutical form and route of administration	Dose	Frequency and/or Regimen
Afinitor [®]	Tablet for oral use	10 mg for patients without hepatic impairment; 7.5 mg for patients with mild hepatic impairment (Child-Pugh grade A) 5 mg for patients with moderate hepatic impairment (Child-Pugh grade B)	Daily

The investigator should promote compliance by instructing the patient to take the study drug exactly as prescribed and by stating that compliance is necessary for the patient's safety and the validity of the study. The patient should be instructed to contact the investigator if he/she is unable for any reason to take the study drug as prescribed.

Tablets

Everolimus will be supplied as 2.5 mg and 5-mg Afinitor[®] tablets. The tablets are packaged in blisters. The tablets should be swallowed whole with a glass of water and should not be chewed or crushed.

For patients with TSC who have SEGA and are unable to swallow tablets whole, the tablet(s) can be dispersed completely in a glass of water (containing approximately 30 mL) by gently stirring until the tablet(s) are fully disintegrated (approximately 7 minutes), immediately prior to drinking. The glass should be rinsed with the same volume of water and the rinse completely swallowed to ensure the entire dose is administered.

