6.2.2 Dosing modifications

For patients who do not tolerate the protocol-specified dosing schedule, dose adjustments are permitted in order to allow the patient to continue the study treatment. Details of study treatment schedule adjustments and dose levels are provided in [Table 6-2](#).

Table 6-2 Study treatment schedule adjustments and dose levels

	Afinitor [®] Starting dose level - 0	Dose level - 1	Dose level - 2
Patients without hepatic impairment	10 mg daily	5 mg daily	5 mg every other day
Patients with mild hepatic impairment (Child-Pugh grade A)	7.5 mg daily	5 mg daily	5 mg every other day
Patients with moderate hepatic impairment (Child-Pugh grade B)	5 mg daily	5 mg every other day	Not permitted

Notes:

- Dose reduction should be based on the worst toxicity demonstrated after the most recent dose received.
- Dose reduction below 5 mg every other day is not allowed. Treatment must be discontinued.

Management of severe or intolerable adverse drug reactions (ADRs) may require temporary dose interruption (with or without dose reduction) or discontinuation of Afinitor[®] therapy. If

dose reduction is required, the suggested dose is approximately 50% lower than the daily dose previously administered.

The lowest permitted Afinitor[®] dose in this study is 5 mg every other day. Patients who don't tolerate 5 mg Afinitor[®] every other day must be discontinued permanently.

Table 6-3 and Table 6-4 summarize the recommendations for dose interruption, reduction, or discontinuation of Afinitor[®] in the management of ADRs. General management recommendations are also provided as applicable. Clinical judgment of the treating physician should guide the management plan of each patient based on individual benefit/risk assessment.

Table 6-3 Dosing guidelines for study drug-related non-hematologic toxicities

Adverse drug reaction	Severity¹	Afinitor[®] dose adjustment² and management recommendations
Non-infectious pneumonitis	Grade 1 Asymptomatic, clinical or diagnostic observations only; intervention not indicated	No dose adjustment required. Initiate appropriate monitoring.
	Grade 2 Symptomatic, medical intervention indicated; limiting instrumental ADL ³	Consider interruption of therapy, rule out infection and consider treatment with corticosteroids until symptoms improve to Grade ≤ 1. Re-initiate Afinitor [®] at a lower dose. Discontinue treatment if failure to recover within 4 weeks.

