6.3 Concomitant medications

Concomitant medications and therapies for adverse events or supportive treatments are permitted. Some medications may however have drug-drug interactions with everolimus and the guidelines below should be followed.

In clinical studies and post-marketing spontaneous reports, angioedema has been reported with and without concomitant use of angiotensin-converting-enzyme (ACE) inhibitors. The risk of angioedema events may be increased with concomitant administration of ACE inhibitors.

Cytochrome P450 and P-glycoprotein (PgP) inhibitors/inducers/substrates

Everolimus is metabolized by CYP3A4 in the liver and to some extent in the intestinal wall.

Therefore, the following are recommended:

- Co-administration with strong inhibitors of CYP3A4/PgP should be avoided and may cause increased everolimus concentrations.
- Co-administration with moderate CYP3A4/PgP inhibitors should be used with caution. If a patient requires co-administration of moderate CYP3A4/PgP inhibitors, reduce the dose of study drug to half the currently used dose. Additional dose reductions may be required to manage toxicities. If the inhibitor is discontinued, consider a washout period of at least 2-3 days (average for the most commonly used moderate inhibitors), before the study drug dose is returned to the dose used prior to initiation of the moderate CYP3A4/PgP inhibitor.
- Co-administration with strong inducers of CYP3A4 should be avoided.
- If a patient requires co-administration of strong CYP3A4 inducer, an increase in the dose of study drug up to twice the currently used daily dose should be considered, using 5 mg increments or less. This dose adjustment of study drug is predicted to achieve similar AUC to the range observed without inducers. However, there are no clinical data with this dose adjustment in patients receiving strong CYP3A4 inducers. If the strong inducer is discontinued, consider a washout period of at least 3-5 days (reasonable time for significant enzyme de-induction), before the study drug dose is returned to the dose used prior to initiation of the strong CYP3A4/PgP inducer.

Please refer to [Table 6-5](#) listing relevant inducers and inhibitors of CYP3A and to [Table 6-6](#) for a list of relevant substrates, inducers, and inhibitors of PgP.

Table 6-5 Clinically relevant drug interactions: inducers, and inhibitors of isoenzyme CYP3A4

Inducers

Strong inducers:

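### The rule to halve the dose with a moderate CYP3A4/PgP inhibitor cannot be followed at two of the four regimens in Table 6-2: it breaches the dose floor at one and needs part-tablets at the other

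*Protocol*

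**What the plan says.** **Interaction rule (Protocol Section 6.3).** For a patient who needs a moderate CYP3A4/PgP inhibitor, the instruction is to "reduce the dose of study drug to half the currently used dose". The list containing it is introduced as recommendations, but the opening of the section says that "the guidelines below should be followed". The same bullet adds: "Additional dose reductions may be required to manage toxicities". It then describes going back to the earlier dose after the inhibitor stops, so it assumes that the patient stays on treatment.

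**Dose floor (Protocol Section 6.2.2).** Table 6-2 sets the starting dose and the reduced levels by hepatic function. Its note reads: "Dose reduction below 5 mg every other day is not allowed. Treatment must be discontinued". The text below the table repeats the limit in general terms, naming the lowest permitted "dose in this study is 5 mg every other day".

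**Tablets (Protocol Section 6.1.1).** "Everolimus will be supplied as 2.5 mg and 5-mg" tablets. On handling: "The tablets should be swallowed whole with a glass of water and should not be chewed or crushed". The exception for patients with SEGA who cannot swallow tablets lets them disperse tablets in water, but the whole amount must be drunk. It gives no route to part of a tablet.

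Section 6.3 does not mention the floor or the tablet strengths.

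**The concern.** A halving rule without exceptions sits beside a fixed minimum dose and a fixed tablet step. At the lowest level the two sections give opposite instructions for the same patient: Section 6.3 says continue at half, and Section 6.2.2 says do not go lower and stop. At 7.5 mg daily there is no clash about stopping, but the halved dose cannot be dispensed.

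Sites could settle either case in different ways. What is at stake is first the patient's exposure and continuation. After that come the summaries of dose adjustments and permanent discontinuations with their reasons (Protocol Section 10.3, SAP Section 2.4.1), in a trial whose primary objective is safety. Protocol Section 12 allows no authorized deviations, so a site that follows Section 6.3 at the lowest level breaches Section 6.2.2.

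**Working it through.** The plan states no figure to reproduce, so the check is direct arithmetic on the regimens in Table 6-2.

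**Inputs**
- Halving factor: 0.5 (Section 6.3).
- Distinct permitted regimens: 10 mg daily, 7.5 mg daily, 5 mg daily and 5 mg every other day (Table 6-2).
- Floor: 5 mg every other day, which is 5 / 2 = 2.5 mg/day on average (Section 6.2.2).
- Tablet step: with whole 2.5 mg and 5 mg tablets, each intake must be a multiple of 2.5 mg (Section 6.1.1).

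**Two tests for each regimen**
1. Tablets: is half of the single intake a multiple of 2.5 mg?
2. Floor: is half of the average daily dose at least 2.5 mg/day?

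| Current regimen | Half of the intake | Whole tablets? | Half of the daily average | At or above 2.5 mg/day? | Can the rule be followed? |
|---|---|---|---|---|---|
| 10 mg daily | 5 mg | yes | 10 / 2 = 5 mg/day | yes | yes, a listed level |
| 7.5 mg daily | 3.75 mg | no (3.75 / 2.5 = 1.5) | 7.5 / 2 = 3.75 mg/day | yes | no, tablet strength |
| 5 mg daily | 2.5 mg | yes | 5 / 2 = 2.5 mg/day | yes, exactly at the floor | yes, equal to 5 mg every other day |
| 5 mg every other day | 2.5 mg | yes | 2.5 / 2 = 1.25 mg/day | no | no, below the floor |

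**Count by cell of Table 6-2**
- No hepatic impairment: three permitted cells (10 mg daily, 5 mg daily, 5 mg every other day). One fails.
- Child-Pugh A: three permitted cells (7.5 mg daily, 5 mg daily, 5 mg every other day). Two fail.
- Child-Pugh B: two permitted cells (5 mg daily, 5 mg every other day). One fails.
- Total: 1 + 2 + 1 = 4 failing cells out of 3 + 3 + 2 = 8, with at least one in every row.

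**Further reductions.** From 5 mg daily the halved dose is already at the floor. The extra reductions for toxicity that Section 6.3 foresees are then not available without discontinuation.

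**The case against.** **The floor is mandatory and the interaction rule is only recommended, so the floor prevails.** This is the strongest reply. Section 6.2.2 prohibits and requires, while the bullets in Section 6.3 are introduced as recommendations, and a careful site could read the floor as limiting the halving. That reading is reasonable, but the text does not state it. Section 6.3 also says that its guidelines should be followed, and it has no exception or cross-reference to the floor.

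**The floor concerns intolerance only.** It does stand in the section on dose changes for intolerance. But the sentence naming the lowest dose speaks of the study as a whole.

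**Reductions need only be about half.** That latitude is written for reductions made for adverse reactions (Section 6.2.2, Table 6-3, Section 6.2.3.5). The interaction rule does not carry it. Alternating daily amounts could average 3.75 mg/day, but neither document provides for such a schedule.

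**Few patients will be affected.** This largely stands for 7.5 mg daily. That is the Child-Pugh A starting dose only, and exclusion criteria 5 and 16c remove much liver disease. It is weaker for the floor conflict, because 5 mg every other day is a permitted level in every hepatic row. Table 6-5 counts erythromycin, ciprofloxacin, diltiazem and verapamil among the moderate inhibitors, so a need for one is plausible, but nothing quantifies it.

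**The SAP's counts are unaffected.** In part. SAP Section 2.4.1 derives reductions from the doses recorded, and its own example includes 2.5 mg daily, which Table 6-2 does not list. An unlisted dose therefore does not break the derivation. What may still vary by site is whether the record shows a reduction or a discontinuation.

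**Conclusion.** The point holds for two of the four distinct regimens, for different reasons: the dose floor at 5 mg every other day, and tablet strength at 7.5 mg daily. The instruction is wrong as written. Severity is minor, because the rule works at the main starting dose and the number of patients affected is unknown and may be small. One patient is 1 / 40 = 2.5% of the trial, but that is only the weight of a single case and says nothing about how often it happens.

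Three stronger readings are tempting, and the documents do not support them:
- *The rule works only at 10 mg daily.* Half of 5 mg daily is 2.5 mg/day on average, which equals the listed next level, "5 mg every other day". Taking 2.5 mg daily gives the same average and is not listed, so there is some ambiguity, but the rule can be met.
- *Every failing case pits continuing against stopping.* At 7.5 mg daily the halved dose stays above the floor and no passage calls for discontinuation. The obstacle is the tablets.
- *The safety results are distorted.* The documents do not show that any patient met either situation, and the analysis is descriptive, without hypothesis testing.

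The count assumes whole tablets, a floor read as an average of 2.5 mg/day, and only the regimens in Table 6-2. Doses raised under Section 6.3 for a strong inducer are left out.

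**What to change.** Reconcile Sections 6.1.1, 6.2.2 (with Table 6-2) and 6.3, so that the interaction instruction, the dose floor and the tablet strengths do not contradict each other at any permitted dose. Which rule should give way is a clinical decision for the sponsor; none is proposed here.

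The cost is a short clarification with notice to sites. SAP Section 2.7.1 already refers to database lock, so for this trial the clarification may come too late to guide sites. The study report can still use the concomitant-medication and dosing records to identify any patient who took a moderate inhibitor while on 7.5 mg daily or 5 mg every other day, and state what was done. If there were none, one sentence closes the point. That takes one listing from data already collected.

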6.4 Patient numbering and treatment assignment

6.4.1 Patient numbering

Each patient is identified in the study by a 7 digit subject number, that is assigned when the patient is first enrolled for screening and is retained as the primary identifier for the patient throughout his/her entire participation in the trial. The subject number consists of the 4-digit center number (as assigned by Novartis to the investigative site) with a 3-digit sequential patient number suffixed to it, so that each subject is numbered uniquely across the entire database. Upon signing the informed consent form, the patient will be assigned the next

available sequential patient number by the investigator or designee. Once assigned to a patient, a patient number will not be reused. If a patient fails screening and is re-screened a new 7 digit subject number will be assigned. If after signing the informed consent, it is determined that the patient does not qualify for the study, reason(s) will be entered on the disposition CRF and Novartis notified.

6.4.2 Treatment assignment

All patients who fulfill all inclusion/exclusion criteria will start receiving study treatment with Afinitor[®]. The investigator will assign patients to the 10 mg, 7.5 mg, or 5 mg O.D. Afinitor[®] dose depending on their hepatic function (no liver impairment, Child-Pugh grade A, Child-Pugh grade B).

6.4.3 Treatment blinding

Not applicable.

6.5 Study drug preparation and dispensation

The investigator or responsible site personnel must instruct the patient or caregiver to take the study drug as per protocol. Study drug will be dispensed to the patient by authorized site personnel only. All dosages prescribed to the patient and all dose changes during the study must be recorded on the Study Treatment CRF.

Table 6-7 Preparation and dispensing

Study treatment	Dispensing	Preparation
RAD001 (everolimus)	Afinitor [®] tablets including instructions for administration are dispensed by study personnel on an outpatient basis. Patients will be provided with adequate supply of study treatment for self-administration at home until at least their next scheduled study visit.	Not applicable

6.5.1 Study treatment packaging and labeling

Study treatment, Afinitor[®], will be sourced as local commercial supply (in the locally approved formulation and packaging configuration) and re-labeled as study drug. Study treatment labels will comply with the legal requirements in China and will include storage conditions, a unique medication number (corresponding to strength).

Table 6-8 Packaging and labeling

Study treatments	Packaging	Labeling (and dosing frequency)
RAD001 (everolimus)	Tablets in blister	Labeled as 'Afinitor [®] /RAD001/everolimus' Study treatment packaging has a 2-part label. A unique medication number is printed on each part of this label.

6.5.2 Drug supply and storage

Study treatments must be received by designated personnel at the study site, handled and stored safely and properly, and kept in a secured location to which only the investigator and designated site personnel have access. Upon receipt, the study treatment should be stored according to the instructions specified on the drug label.

6.5.3 Study drug compliance and accountability

6.5.3.1 Study drug compliance

Compliance will be assessed by the investigator and/or study personnel at each patient visit and information provided by the patient and/or caregiver will be captured in the Drug Accountability Form. The Afinitor[®] dose that each patient is taking will be recorded on the Study Treatment CRF. This information must also be captured in the source document at each patient visit.

The investigator and/or assigned study personnel will also collect any information about concomitant medications and non-drug therapies at each patient visit and enter it on the ‘Concomitant Medication / Non-drug Therapies’ CRF page.

6.5.3.2 Study drug accountability

The investigator or designee must maintain an accurate record of the shipment and dispensing of study treatment in a drug accountability log. Drug accountability will be noted by the field monitor during site visits and at the completion of the study. Patients will be asked to return all unused study treatment and packaging on a regular basis, at the end of the study or at the time of study treatment discontinuation.

At study close-out, and, as appropriate during the course of the study, the investigator will return all used and unused study treatment, packaging, drug labels, and a copy of the completed drug accountability log to the Novartis monitor or to the Novartis address provided in the investigator folder at each site.

6.5.4 Disposal and destruction

The study drug supply can be destroyed at the local Novartis facility, Drug Supply group or third party, as appropriate. If study medication is to be destroyed by a third party or at the investigational site this must be approved by the sponsor and destruction certificates must be provided.

7 Visit schedule and assessments

7.1 Study flow and visit schedule

Table 7-1 lists all of the assessments and indicates with an “X” the visits when they are performed. All data obtained from these assessments must be supported in the patient’s source documentation.

The table indicates which assessments produce data to be entered into the clinical database (D) or remain in source documents only (S) (“Category” column). No CRF will be used as a source document.

Allowed visit windows are specified as follows:

- Screening assessments as listed in Table 7-1 should occur within 28 days prior to Day 1.
- The 4, 12, 24, and 48 weeks visits should be performed within a ± 7 day window.

[figure not shown]
- The 12, 24, and 48 weeks efficacy follow-up visits, where applicable, should be performed within a ± 7 day window.
- Urine pregnancy tests (when applicable) should be performed every 4 weeks during the treatment phase within a ± 7 day window.
- The End of Treatment (EOT) visit should be performed within 28 days of last dose.
- All patients should be followed for at least 30 days for AEs and SAEs after last dose.

Every effort should be made to follow the schedule outlined in [Table 7-1](#).

[figure not shown]

Table 7-1 Visit evaluation schedule

[figure not shown]
Visit Name	Category	Protocol Section	Screening	Open Label Treatment								Treatment Discontinuation Follow-up
				Day 1	Week 4	Week 12	Week 24	Week 48	Every 4 weeks after Week 4 until EOT	End of study treatment (EOT)	Safety follow-up (Last dose +30days)	
Visit number			1	100	110	120	130	140		1999		1010,1020,1030
Visit window			-28 to -1 days		±7days	±7days	±7days	±7days	±7days	Within 28 days from last dose	+7 days	±7days
Obtain Informed Consent	D	11.3	X									
Demography	D	7.1.2.3	X									
Inclusion/exclusion criteria	D	5.2 5.3	X	X								
TSC diagnosis	D	7.1.2	X									
Relevant medical history	D	7.1.2.3	X									
HIV history	S	7.1.2.3	X									
Prior/concomitant medications	D	7.1.2.3	X	X	X	X	X	X		X	X	
Physical examination	S	7.2.2.1	X	X	X	X	X	X		X		
WHO Performance status	D	7.2.2.4	X	X	X	X	X	X		X		
Height	D	7.2.2.3	X									
Weight	D	7.2.2.3	X	X	X	X	X	X		X		

[figure not shown]
Visit Name	Category	Protocol Section	Screening	Open Label Treatment								Treatment Discontinuation Follow-up	
				Day 1	Week 4	Week 12	Week 24	Week 48	Every 4 weeks after Week 4 until EOT	End of study treatment (EOT)	Safety follow-up (Last dose +30days)		
Visit number			1	100	110	120	130	140		1999		1010,1020,1030	
Visit window			-28 to -1 days		±7days	±7days	±7days	±7days	±7days	Within 28 days from last dose	+7 days	±7days	
Vital signs	D	7.2.2.2	X	X	X	X	X	X		X			
Hematology	D	7.2.2.5	X	X	X	X	X	X		X			
Biochemistry	D	7.2.2.5	X	X	X	X	X	X		X			
Coagulation	D	7.2.2.5	X	If clinically indicated							If clinically indicated		
Pulmonary function tests (FEV1, DLCO) for LAM patients only	D	7.2.2.6	X			X	X	X		X			
Blood gas analysis (O ₂ saturation) for LAM patients only	D	7.2.2.6	X			X	X	X		X			
HCV-RNA, HBV-DNA, HBsAg, HBsAb, HBcAb	D	7.1.2	X										
Urinalysis	D	7.2.2.5	X	X	X	X	X	X		X			
ECG	D	7.1.2	X	If clinically indicated									
Serum pregnancy test	D	7.1.2.3	X							X			

	Category	Protocol Section	Screening	Open Label Treatment								Treatment Discontinuation Follow-up
				Day 1	Week 4	Week 12	Week 24	Week 48	Every 4 weeks after Week 4 until EOT	End of study treatment (EOT)	Safety follow-up (Last dose +30days)	
Visit Name			Screening	Day 1	Week 4	Week 12	Week 24	Week 48	Every 4 weeks after Week 4 until EOT	End of study treatment (EOT)	Safety follow-up (Last dose +30days)	Efficacy follow-up (Week 12, 24, 48)
Visit number			1	100	110	120	130	140		1999		1010,1020,1030
Visit window			-28 to -1 days		±7days	±7days	±7days	±7days	±7days	Within 28 days from last dose	+7 days	±7days
Urine pregnancy test	S	7.2.2.5.5		X	X	X	X	X	X			
Abdomen and pelvis CT/MRI	D	7.2.1	X			X	X	X		X		X
Brain MRI/CT	D	7.2.1	X			If clinically indicated				If clinically indicated		If clinically indicated
Chest CT	D	7.2.1	If clinically indicated			If clinically indicated				If clinically indicated		If clinically indicated
Digital photography of skin lesions	D	7.2.1	If present			If identified at screening				If identified at screening		If identified at screening
Adverse events	D	8.1	X	X	X	X	X	X		X	X	
Serious adverse events	D	8.2	X	X	X	X	X	X		X	X	
Study Drug administration	D	6.1.1		X	X	X	X	X		X		
End of phase Disposition	D									X		X

	Category	Protocol Section	Screening	Open Label Treatment								Treatment Discontinuation Follow-up
				Day 1	Week 4	Week 12	Week 24	Week 48	Every 4 weeks after Week 4 until EOT	End of study treatment (EOT)	Safety follow-up (Last dose +30days)	
Visit Name			Screening	Day 1	Week 4	Week 12	Week 24	Week 48	Every 4 weeks after Week 4 until EOT	End of study treatment (EOT)	Safety follow-up (Last dose +30days)	Efficacy follow-up (Week 12, 24, 48)
Visit number			1	100	110	120	130	140		1999		1010,1020,1030
Visit window			-28 to -1 days		± 7days	± 7days	± 7days	± 7days	± 7days	Within 28 days from last dose	+7 days	± 7days
Antineoplastic therapies since discontinuation of study treatment	D									X	X	X

